Full Title: Efficacy potential of goal management training to improve cognitive

function in older people living with HIV

Abbreviated title: Goal Management training in people living with HIV

Version Number: V1.0

Date of Protocol: April 8, 2016

Funding: Canadian Foundation for AIDS Research (CANFAR)

Principal Investigators: [name] & [name]

Chronic Viral Illness Service of the Royal Victoria Hospital

McGill University Health Centre

Glen site

[name]

Associate investigators: [name]

Neuropsychologist

Professor in the Department of Psychology and Medicine

University of Toronto

Data Management Group: [name]

Royal Victoria Hospital, Room 4.29

[name] The Rotman Research Institute Baycrest Centre for Geriatric Care

[name]

[name]

PROTOCOL SUMMARY

Full Title	Efficacy potential of goal management training to improve cognitive function in older people living with HIV
Short title	Goal Management training in people living with HIV
Sponsor	McGill University Health Centre
Funding	Canadian Foundation for AIDS Research (CANFAR)
Principal Investigators	[name] & [name]
Associate investigators	[name] & [name]
Primary Objectives	Determine the feasibility and acceptability of GMT in people with stable HIV infection who report cognitive concerns
	2. Provide preliminary evidence of the effect of GMT on cognitive performance, compared to a waitlist control group, as measured by (i) cognitive performance tests and (ii) self-report questionnaires
Study Population	 Age ≥ 45 HIV infection for at least 1 year Able to communicate in English or French Capable of providing informed consent Subjective complaints of cognitive difficulties Evidence of cognitive deficit (B-CAM score ≤ 24) Exclusion Criteria Dementia (MSK-rating stage 3 or more-cognitive component only) Concern about capacity to consent Life expectancy of < 3 years or other personal factor limiting the ability to participate in follow-up Non-HIV-related neurological disorder likely to affect cognition Known active CNS opportunistic infection or hepatitis C requiring IFN treatment during the follow-up period Known psychotic disorder Current substance dependence or abuse within the past 12 months.
Study Design	Observational
Sample Size	60
Study Duration	1 year

Contents

PROTOCOL SUMMARY	2
EFFICACY POTENTIAL OF GOAL MANAGEMENT TRAINING TO IMPROVE COGNITIVE FUI	
Background information	
Clinical Significance	5
Study Hypothesis	5 6
Study Objectives	6
STUDY DESIGN	6
Procedure	6
Intervention	6 7
TREATMENTS	7
STUDY EVALUATIONS/PROCEDURES	7
Informed Consent	7
Subject Identification Number Assignment	7
DETAILS OF STATISTICAL ANALYSIS	
Analysis and Sample Size	7
REFERENCES	q

EFFICACY POTENTIAL OF GOAL MANAGEMENT TRAINING TO IMPROVE COGNITIVE FUNCTION IN OLDER PEOPLE LIVING WITH HIV

Background information

People living with HIV worry about their memory, and with good reason. It is now clear that this chronic illness can have disabling effects on cognition, even with excellent systemic viral control (1). Although the burden of cognitive impairment in HIV in Canada is unknown, it is likely to be high. Recent studies in other developed countries, using comprehensive neuropsychological assessment, report a prevalence of (primarily mild) cognitive impairment of 30-50% (1, 2). Even higher rates have been documented in those over the age of 50, a rapidly expanding group at the frontier of existing knowledge about the combined effects of aging and longstanding HIV infection (3). Impaired cognition can affect medication adherence (in turn posing a public health risk for the spread of HIV), occupational and social function, quality of life, and even accelerate mortality (4, 5). We are only beginning to understand this emerging co-morbidity, which is likely the result of multiple interacting processes, including chronic neuroinflammation, premature cerebrovascular disease, neurotoxic effects of drug treatment, and co-existing mental health issues (1).

Given these hypotheses, the field has assumed that cognitive impairment in HIV is likely to be progressive, in fact our own work using the CHARTER data shows this is not generally the case. Although 246/701 in the longitudinal cohort were classified as cognitively impaired at baseline, only 16% (N=111) showed decline at 3 years, most of the time on a single neuropsychological test. This observation suggests that for the majority of people, mild cognitive impairment may be a relatively static condition. On-going work in several countries aims to better understand the factors contributing to cognitive impairment in older people with HIV, including a CIHR-funded project we are currently leading [Positive Brain Health Now (+BHN), http://brainhealthnow.mcgill.ca]. However, we need not wait for a full understanding of the determinants of cognitive impairment to take action; patients with these difficulties need solutions now. Testing the impact of available interventions can establish what works, and can also help us understand whether the impact of brain injury in HIV can be mitigated to preserve function and quality of life.

Rehabilitation is a well-established approach to maintain function in the face of chronic disease, and holds promise for addressing the health challenges faced by older people with HIV (6). A Canadian-led knowledge synthesis review published in 2014 identified cognitive rehabilitation as a promising approach in HIV, but highlighted the absence of high quality, HIV-specific evidence in this area (7). A recent focused review also highlights the dearth of evidence on this topic (8). Very few studies have been published, and to date all have been restricted to computerized training programs only (8). While there is limited evidence for computerized cognitive rehabilitation in any context, there is better evidence for more conventional, in-person rehabilitation approaches, at least in other neurological disorders. Although computerized training is appealing because it is more feasible to deliver on a wide scale than conventional cognitive rehabilitation, we propose that the first step should be to establish an evidence base regarding the efficacy of any form of cognitive rehabilitation in HIV. Evidence of efficacy of a 'high dose' established rehabilitation method could be followed by work to define the key elements, and to study how those elements could be delivered most cost-effectively, but there is no point in pursuing these secondary steps if the most well-established cognitive rehabilitation approaches do not show efficacy. Thus, we propose to test conventional rehabilitation as a crucial first step is a research program focused on evidencebased interventions for improving brain health in HIV.

There is no gold standard conventional cognitive rehabilitation program, but most existing approaches combine face-to-face therapy with at home practice over a period of at least several weeks. In the absence of a gold standard, we have selected one such program: Goal Management Training (GMT). This

program targets executive dysfunction, which is a central problem in HIV-associated neurocognitive disorder (8, 9). GMT is grounded in a neurobiological framework and was developed based on nearly two decades of research on practical approaches to minimizing the impact of executive dysfunction, aiming to help people with brain injury manage real life tasks. The program teaches self-management principles, stress management and mindfulness, and trains participants in the use of several explicit strategies to reduce cognitive load in everyday tasks, and methods to cue attention to maintain focus on specific tasks. GMT is now a manualized protocol with set content conveyed through a combination of slides and a workbook. Two-hour small group sessions are led, in person, by a trained therapist either once twice a week, for seven weeks. The small group sessions allow participants to learn from each other, enhancing engagement. GMT has been shown to improve cognitive function in a variety of neurological conditions, as well as in healthy older people with cognitive concerns (10-13). Evidence from randomized trials shows that this intervention leads to (i) significant improvements in performance on cognitive tests, including naturalistic tests of real life tasks, (ii) reduced self-reported cognitive concerns (10, 11, 14), and (iii) significant improvements in everyday function (11-13, 15) compared to either a wait-list condition or a general brain health education control. Positive effects have been found in older people with cognitive concerns, and neurological populations with mild cognitive impairment including mild traumatic brain injury (10), stroke (11) and spina bifida (14, 15). These improvements have been shown to last at least 6 months in some studies (13-15) and are accompanied by changes in the brain networks underlying executive function (16). GMT is thus a well-validated, high yield intervention with which to test the potential of cognitive rehabilitation in older HIV+ people with cognitive concerns.

Clinical Significance

The proposed project brings together a high profile multidisciplinary team to perform the first randomized controlled study of in-person cognitive training in the HIV population. The core platform is a low burden observational study that aims to understand and address the heterogeneous, multi-factorial nature of compromised brain health in people living with HIV. The pilot project is cost- and time-effective, nested within this ongoing observational cohort study. A standardized intervention will be used, supported by good evidence of efficacy in studies involving other neurological disorders with similar profiles of cognitive impairment. [name] (co-I) had a pivotal role in the validation of the GMT intervention and is an expert in the area of cognitive training. Our team also has extensive experience with all of the project requirements, including HIV clinical trials, large-scale health outcomes research, data management, and advanced statistical methodologies. Addressing or preventing cognitive impairment is a pressing concern for people living with HIV, and those who care for them. Cognitive training is resource consuming and not the standard of care in HIV. High quality evidence is needed to justify committing resources to such training. We propose work that directly addresses this need, taking advantage of the 'window of opportunity' provided by the on-going +BHN project. Regardless of the outcome, this study will provide important information to orient future work aiming to improve cognition in people living with HIV. The results of this pilot study will inform the development of a full randomized controlled trial.

Study Hypothesis

We hypothesize that GMT, a cognitive rehabilitation intervention, will lead to improved cognitive function as assessed by better performance on cognitive tests and reduced cognitive concerns in people with stable HIV infection who report cognitive concerns at baseline, compared to a wait-list group.

Study Objectives

The specific objectives of this study are to:

- 1. Determine the feasibility and acceptability of GMT in people with stable HIV infection who report cognitive concerns
- 2. Provide preliminary evidence of the effect of GMT on cognitive ability, as measured by changes in (i) cognitive performance tests and (ii) self-report questionnaires.

STUDY DESIGN

This is a concurrently controlled trial. Study participants will be randomly selected from those participating in the ongoing, longitudinal +BHN study at 2 sites in Montreal (The Montreal Chest Institute and L'Actuel Medical Clinic). This CIHR Team Grant-supported observational, prospective cohort study is enrolling consecutive patients attending 5 HIV clinics across Canada for a total sample of 900, followed every 9 months for 27 months. Inclusion criteria are: age 35 y or older, HIV infection for at least 1 year, able to communicate in English or French and capable of providing informed consent. Exclusions are presence of dementia, life expectancy < 3 y, other neurological disorder including active opportunistic CNS infection, psychotic disorder, current substance dependence or abuse, and Hepatitis C requiring interferon therapy during the study period. Montreal sites will enroll 350 participants, which should provide an adequate pool for recruitment to this sub-study.

The GMT intervention will be tested in a randomly selected sub-group (N=30) of this cohort who meet the following additional criteria: over age 45, subjective complaints of cognitive difficulties, and performance on objective computerized cognitive tests that falls at or below the 50th percentile of performance in the cohort as a whole (as measured by the cohort study's primary outcome, a combination of self-report and performance items called the Brief Cognitive Ability Measure [B-CAM] (17)). The concurrent control group will be comprised of those eligible for GMT but not randomly selected.

Procedure

Participants will be recruited at the time of their routine +BHN study visit, at which comprehensive information about their current health status, function, quality of life, cognitive concerns, and cognitive performance is already being gathered. Following informed consent, all participants will complete a short set of neuropsychological tests and questionnaires that have been shown to be sensitive to the effects of GMT [Sustained Attention to Response Task-SART (18),Tower of London (19), and Dysexecutive Questionnaire-DEX (20)] immediately, or at a visit arranged for this purpose, separate from the +BHN main study. Participants will then begin GMT, as described below. Within 4 weeks of completing the GMT program, they will be asked to repeat the neuropsychological testing and complete additional tests which form part of the standard +BHN visit at a second study visit, coincident with the +BHN study visit if timing permits.

Intervention

The standard GMT program lasts 9 weeks and involves 9 weekly 2-hour small group sessions led by a trained therapist. It follows a manualized program that teaches participants a series of techniques to build attention and executive function, and shows them how to implement these techniques in their everyday life. The small group sessions allow individualization of the training to show how it can be applied to

meet the particular challenges reported by participants, and explicitly encourage participants to share their challenges and successes with others in the group to promote learning and engagement with the program. The sessions are reinforced with homework, in which participants practice what they have learned. Sessions will be audiotaped for later review by the trainer and/or study investigators to ensure adherence to the intervention manual. The material, including homework, is provided in a workbook that participants use throughout the training, and keep for later reference.

TREATMENTS

There are no pharmacological treatments involved in the current study.

STUDY EVALUATIONS/PROCEDURES

Informed Consent

The subject will be asked to read and sign the approved informed consent form prior to any assessments being performed. Sufficient opportunity will be given to discuss the study and consider the information in the consent process prior to agreeing to participate. The original signed informed consent form will be retained in the subject's study files and a copy will be provided to the subject.

Subject Identification Number Assignment

Subject Identification (ID) numbers assigned for the core platform will be used for this sub-study.

DETAILS OF STATISTICAL ANALYSIS

Analysis and Sample Size

The feasibility and acceptability of the GMT will be evaluated in the whole group (N=30) based on the proportion of GMT sessions attended, the proportion of the homework completed, and the overall level of satisfaction with the program, as determined by an anonymous questionnaire filled out by the participants at the end of the intervention.

The potential impact on cognition of GMT will be evaluated in two ways: (i) a within-person analysis of change in cognitive outcomes after all persons have completed the GMT program; and, for exploratory purposes, (ii) a between group comparison contrasting change in cognitive outcomes between the GMT group and the concurrent control group assessed in the main study.

For all analyses, the B-CAM (performance measure) will be the primary cognitive outcome and a global outcome response will be based on changes in the B-CAM and on four secondary cognitive outcome measures: SART, Tower of London, Dysexecutive Questionnaire-DEX and PDQ.

For the within-person analysis, change from pre-to post will be calculated for each person and a 95% confidence interval (CI) around the mean change will be calculated. A 95% CI that excludes 0 indicates statistically significant change. A sample size of 30 will provide 80% power to detect an average standardized response mean (effect size for change) of 0.38, within the reported range for GMT in other conditions. However, average change is not very interpretable as this average change can occur in many ways including no change for a lot of people and large change for a few, or even deterioration for some. To provide a more interpretable estimate of treatment impact, an overall effect will also be reported, based

on the proportion of individuals who improved at least 0.5 SD on one of the cognitive outcome measures. A change of 0.5 SD is considered clinically relevant (21). For this analysis, generalized estimating equations (GEE) will be utilized to adjust for a possible correlation between the different measures. The outcome will be the binary response for each of the five cognitive outcomes, and the analysis yields an estimated charge proportion adjusted for non-independence. Having five outcome measures increases the number of observations available for analysis by a factor of 1.8, termed the design effect. The design effect (22) is a function of the number of measures (here m-1) and the correlation between measures (estimated at 0.2). Hence the number of observations effectively available for analysis is 30 x 1.8 or 54. With this sample size, the 95% CI will exclude a low responder proportion (20%) as long as the responder proportion is greater than 28% (www.vassarstats.net).

For the between-group analysis, 30 people in the intervention group and a concurrent control group of 100 (with five outcome measures, the effective sample size is inflated by the design effect of 1.8). Thus, using all measures, the sample would provide 80% power to detect an effect size of 0.4 (0.4 of a SD). For this analysis, generalized estimating equations (GEE) for a continuous outcome will be utilized to adjust for a possible correlation between the different measures. Each measure will be transformed onto a 0 to 100 scale for permit a global intervention effect to be estimated.

REFERENCES

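### The Protocol Summary's sample size of 60 and waitlist comparator do not match the design and analysis sections, which use 30 GMT participants and an exploratory comparison with about 100 non-selected cohort members

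*Combined protocol and SAP*

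**What the plan says.** Two accounts of the study stand side by side.

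**Summary and hypothesis.** The Protocol Summary table states "Sample Size 60", with no split or derivation, and defines the second primary objective as an effect "compared to a waitlist control group". The Study Hypothesis, in the body, expects improvement "compared to a wait-list group".

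**Design and analysis.** Study Design says: "The GMT intervention will be tested in a randomly selected sub-group (N=30) of this cohort". It continues: "The concurrent control group will be comprised of those eligible for GMT but not randomly selected". Procedure follows baseline testing with "Participants will then begin GMT, as described below" and describes no deferred start. Analysis and Sample Size evaluates feasibility in a whole group of 30 and lists within-person change as the first cognitive analysis. It labels the between-group comparison exploratory and takes its controls from those assessed in the main cohort study. That comparison is sized on "30 people in the intervention group and a concurrent control group of 100", with 80% power claimed for 0.4 SD.

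Study Objectives, also in the body, words objective 2 without a comparator: "Provide preliminary evidence of the effect of GMT on cognitive ability, as measured by changes in" performance tests and questionnaires.

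**The concern.** Sample size and comparator are basic facts of a design, and here each has two values. A reader of the summary expects a 60-person waitlist comparison. The operational sections describe 30 treated people, with eligible cohort members who were not drawn serving as controls.

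The two comparators do not support the same conclusion. Waitlist controls ordinarily enter the sub-study, follow its assessment schedule and expect the intervention later. The controls described here are followed in the cohort, whose visits are 9 months apart, while GMT participants are retested within 4 weeks of finishing. Precision differs too, so the 0.4 SD attached to 30 versus 100 cannot be read as applying to 60 people. The pilot is meant to inform a full randomized trial, and its result could be carried forward as a waitlist comparison when it was not one.

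**Working it through.** **1. Can 60 be derived from the body?** The numbers analysed are 30 (feasibility and within-person) and 30 + 100 = 130 (between-group). Neither is 60. The most natural reconciliation is 30 immediate plus 30 delayed starters, all eventually trained. The feasibility and within-person sets would then be 60, where the plan says 30. The control group would be 30, where the plan says 100.

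**2. Does any stated power figure rest on 60?** Inputs from Analysis and Sample Size: standardized response mean 0.38 at 80% power for the within-person analysis; 0.4 SD at 80% for the between-group analysis; multiplier 1 + (5 − 1) × 0.2 = 1.8. Two-sided 5% is my assumption for the between-group analysis. The plan's 95% interval is given for the within-person analysis, and no alpha or sidedness is stated for the other.

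- Within-person, detectable = (1.96 + 0.842)/√n. This gives 0.51 at n = 30, 0.38 at n = 30 × 1.8 = 54, and 0.36 at n = 60. The stated 0.38 matches 54, not 60.
- Between-group, detectable = (1.96 + 0.842) × √(1/n₁ + 1/n₂). With the multiplier, 54 versus 180: 2.802 × √(0.01852 + 0.00556) = 2.802 × 0.1552 = 0.43 SD (0.44 by noncentral t). This rounds to the stated 0.4, although power at exactly 0.4 is 73%. One-sided, the detectable value is 0.39 SD and power at 0.4 is 82%. The stated figure therefore belongs to 30 versus 100, not to 60.

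**3. What each design detects** (two-sided 5%, noncentral t):

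| Design | Basis | Detectable at 80% power | Power at 0.4 SD |
|---|---|---|---|
| 30 v 100 | one outcome | 0.59 SD | 48% |
| 54 v 180 | plan's 1.8 multiplier | 0.44 SD | 73% |
| 30 v 100 | mean of five measures | 0.35 SD | 89% |
| 30 v 30 (assumed split) | one outcome | 0.74 SD | 33% |
| 54 v 54 (assumed split) | plan's 1.8 multiplier | 0.54 SD | 54% |
| 30 v 30 (assumed split) | mean of five measures | 0.44 SD | 72% |

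The five-measure rows multiply the one-outcome figure by √(1.8/5) = 0.6: 0.59 × 0.6 = 0.35 and 0.74 × 0.6 = 0.44. They assume correlation 0.2, the same standardized effect on every measure, and all five measures available in both groups.

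**The case against.** The strongest defence is that the operational text agrees with itself. Study Design, Procedure, and Analysis and Sample Size all point to 30 trained participants and non-selected controls, so the conflict is confined to the summary and one hypothesis sentence. Feasibility is objective 1, the study is a pilot, and the between-group comparison is labelled exploratory. Objective 2 as worded in the body names no comparator and fits the within-person analysis. All of this stands and limits the consequence. It does not remove the conflict: the summary's primary objective and the body's own hypothesis are both comparative against a waitlist that no section provides.

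A reader might infer more than the documents support:

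- *That 60 people could not reach 0.4 SD on any reading.* This is not so. With a 30/30 split, five measures averaged and a one-sided 5% test, the detectable difference is 0.65 × 0.6 = 0.39 SD, with power 82% at 0.4. The shortfall holds for the two-sided readings, which are the natural default but are not stated for this analysis.
- *That 0.4 SD is the plan's only detectable effect.* It is the only between-group one. The within-person analysis has its own (0.38), and there is also a responder-proportion criterion.
- *That controls will certainly never receive GMT.* This is inferred from silence. The within-person analysis is to follow once everyone has finished GMT, which could be a remnant of a waitlist design, but the whole group is given as 30 and no delayed arm appears.

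**Conclusion.** The point holds as an internal inconsistency. The summary's 60, and the waitlist in the summary and the hypothesis, do not describe the study that the design and analysis sections set out. It is not that objective 2 goes unanalysed: the mismatch is with the summary's wording of it, and the within-person analysis serves the body's wording.

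At two-sided 5% and 80% power, the described 30 versus 100 detects about 0.59 SD on B-CAM alone and about 0.44 SD with the plan's multiplier. A 60-person waitlist trial would detect about 0.74, 0.54 or 0.44 SD (one outcome, 1.8 multiplier, five-measure mean). These last figures rest on an assumed 30/30 split; the documents do not say what the 60 counts. The inconsistency itself depends on none of the power figures. It should be corrected, because sample size and comparator determine how the result is described.

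**What to change.** State one design throughout.

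**If the described design is the real one:** in the Protocol Summary and Study Hypothesis, replace 60 and the waitlist with 30 people selected for GMT and about 100 eligible non-selected cohort members as concurrent controls, and mark the comparison as exploratory. In Analysis and Sample Size, give the between-group detectable difference for those numbers with its alpha and sidedness: about 0.59 SD on B-CAM alone, or about 0.44 SD with the 1.8 multiplier, at two-sided 5% and 80% power. The cost is wording and a less favourable stated figure, with no extra patients.

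**If 60 with a waitlist is the real one:** Study Design, Procedure, and Analysis and Sample Size must all be reconciled to it, including the start of GMT, the whole-group number and the source of controls. The split must be stated, and the 0.4 SD claim must be recalculated, not carried over. This branch is not free, because more people would have to be tested and later trained.

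### The exploratory GMT-versus-cohort contrast compares consenters with all non-selected eligible people, probably over unequal retest intervals, so random selection does not protect it

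*Combined protocol and SAP*

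**What the plan says.** The Study Design section opens with "This is a concurrently controlled trial". It continues: "The GMT intervention will be tested in a randomly selected sub-group (N=30) of this cohort", subject to extra criteria on age, complaints and B-CAM. Of the comparison group it says: "The concurrent control group will be comprised of those eligible for GMT but not randomly selected". The parent +BHN cohort is "followed every 9 months for 27 months".

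The Procedure section recruits at a routine cohort visit and then states: "Following informed consent, all participants will complete a short set of neuropsychological tests and questionnaires". Next comes "Participants will then begin GMT, as described below", and after the course: "Within 4 weeks of completing the GMT program, they will be asked to repeat the neuropsychological testing". That second visit is to coincide with a cohort visit where scheduling allows. The Intervention section gives a 9-week programme; the Background gives seven weeks.

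Analysis and Sample Size plans, as an exploratory analysis, "a between group comparison contrasting change in cognitive outcomes between the GMT group and the concurrent control group assessed in the main study". It sizes this contrast at 30 against 100 and analyses five measures together by GEE. No adjustment for retest interval is stated.

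Other parts describe a different comparator. The Protocol Summary has a waitlist control, a sample of 60 and an observational design. The Study Hypothesis also refers to a wait-list group. Clinical Significance calls the project a randomised controlled study.

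**The concern.** Random selection makes everyone selected comparable with everyone not selected. It does not make selected people who agree to a multi-week course comparable with all non-selected people, some of whom would have refused. A selected person who declines appears to fall in neither group: not in the GMT group, because no GMT was received, and not in the control group, because they were selected. This is an inference, since the documents do not mention decliners.

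Timing is a second difference. If one group is re-tested sooner, practice effects and natural change can differ between the groups even if everybody consents.

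The hypothesis is comparative, and this is the only planned analysis with a comparison group. The pilot is also meant to inform a full randomised trial. A difference that partly reflects willingness to attend, or the retest interval, could be carried into that trial as though it were a randomised estimate of the GMT effect.

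**Working it through.** **1. The plan's own figure.** Analysis and Sample Size gives 80% power for 0.4 SD, using 30 and 100 people inflated by 1.8.
- Factor: 1 + (5 − 1) × 0.2 = 1.8, so 54 versus 180.
- Standard error: √(1/54 + 1/180) = 0.155 SD.
- Two-sided 5% (assumed; sidedness is not stated for this contrast): detectable effect (1.960 + 0.842) × 0.155 = 0.435 SD; power for 0.4 SD is 73.2%.
- One-sided 5%: 0.386 SD and 82.5%.

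The stated figure is matched only after rounding. That is a separate matter, and nothing below rests on it.

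**2. Who is in each group, as written.**

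| | GMT group | Control group |
|---|---|---|
| Eligible | yes | yes |
| Randomly selected | yes | no |
| Sub-study consent | required | not mentioned |
| Source of outcome | visit after the course | main cohort visits |

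The groups differ by consent as well as by selection.

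**3. Retest intervals.** Inputs: cohort visits every 9 months (9 × 52.18/12 ≈ 39 weeks); programme 9 weeks; re-test 0 to 4 weeks after it. With a wait of w weeks from the recruiting visit to the start of GMT, the GMT interval for B-CAM is w + 9 to w + 13 weeks, because its baseline is the recruiting cohort visit. The documents do not give w, so 8 and 16 weeks are assumptions.

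| Wait w (weeks) | GMT interval (weeks) | 39 ÷ interval |
|---|---|---|
| 0 (limit) | 9–13 | 3.0–4.3 |
| 8 | 17–21 | 1.9–2.3 |
| 16 | 25–29 | 1.3–1.6 |

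The intervals match only if w is 39 − 13 = 26 to 39 − 9 = 30 weeks. With the Background's seven-week course, re-test is at w + 7 to w + 11 and the matching wait is 28 to 32 weeks. The Procedure plans no such delay.

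**4. How large consent bias would have to be.** Illustrative model: bias = q × D, where q is the refusal share and D is the difference in untreated change between acceptors and decliners. For a bias of 0.1 SD, a quarter of the 0.4 SD target, D = 0.1/q:

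| Refusal q | D needed |
|---|---|
| 10% | 1.0 SD |
| 20% | 0.5 SD |
| 40% | 0.25 SD |
| 50% | 0.2 SD |

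The documents give neither q nor D. Consent alone matters only if refusal is substantial.

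**5. Measures available.** The five outcomes are B-CAM, SART, Tower of London, DEX and PDQ. The Procedure gives SART, Tower of London and DEX only after sub-study consent. Controls taken from the main study would have none of these three, so the five-measure between-group GEE cannot be run for them.

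**6. What an analysis by selection could show.** B-CAM only, 30 selected versus 100 not selected, so the factor of 1.8 does not apply.
- 95% CI half-width: 1.96 × √(1/30 + 1/100) = 1.96 × 0.208 = 0.41 SD. With baseline adjustment, multiply by √(1 − r²): 0.35 SD at an assumed r = 0.5 and 0.29 SD at r = 0.7.
- Power (two-sample t, two-sided 5%, effect 0.4 × uptake, unadjusted): 47.9% at full uptake, 33.2% at 80%, 20.8% at 60%, 15.9% at 50%.

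**The case against.** **The contrast is already hedged.** It is labelled exploratory, the design is called concurrently controlled, and the Procedure tries to align visits. This stands, and it lowers the priority. It does not settle the matter, because the hypothesis is comparative and no other planned analysis has a comparison group.

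**The controls may really be a consented waitlist.** The Summary and the Hypothesis say waitlist, and the within-person analysis is to follow once everyone has completed GMT. Planning five measures for controls also suggests that they would be tested in the sub-study. If so, the consent point largely goes, and the timing point goes too if both groups share a schedule. But the sections from Study Design onward describe neither a waitlist procedure nor selection after consent. The contradiction is therefore the first thing to resolve.

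**The interval gap can be overstated.** A reader might take the controls' interval to be three to four times as long. That holds only with no wait before GMT, and small groups take time to assemble. The documents support an inequality that is probable, not one of that size.

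**The added analysis has low yield.** It is imprecise and answers a different question, the effect of being offered GMT. Both points are fair. It is still worth adding because it is the comparison that random selection supports and its data are already collected.

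**Conclusion.** The point holds for the 30-versus-100 design as written: the exploratory contrast does not have the protection of random selection. It rests on two readings of the text: that consent applies only to the GMT side, and that controls are assessed on the cohort schedule. Unequal retest intervals are probable rather than certain.

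A reader might infer that the contrast is biased in favour of GMT, or biased by a material amount. The documents do not support either. They give no refusal rate, no practice effect and no start date, and the Background suggests that mild impairment may be fairly static, so any bias could be small. Nor does the point reach the within-person analysis or the feasibility and acceptability measures.

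This is a cheap improvement of low-to-moderate priority.

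**What to change.** 1. **Reconcile the design.** Set the waitlist control, the sample of 60 and the completion of GMT by everyone against the 30 and 100 cohort controls. State whether selection comes before or after consent, and which measures controls complete. Reconcile the seven-week and 9-week descriptions. If controls consent and are tested on the same schedule, the remaining steps are largely unnecessary.

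2. **If 30 versus 100 stands, add one exploratory B-CAM estimate with 95% CI.** Compare everyone selected, including decliners and dropouts still in +BHN, with everyone eligible and not selected. Measure from the cohort visit of the random draw to the next scheduled visit, adjusting for baseline B-CAM. Leave out of both groups people drawn at their 27-month visit, who have no later scheduled visit. Keep a log of who was selected and when, and report the number without an outcome in each group.

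3. **Limit any early GMT-versus-control contrast** to measures that both groups actually have. Do not carry over the factor of 1.8 or the 80% power. Describe the contrast as non-randomised and report each group's retest interval.

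The cost is wording, the selection log and confirmation that decliners' cohort data may be used on the same basis as the controls'. Precision is low, and refusals dilute the estimate. The outcome visit may come up to 39 − 9 = 30 weeks after GMT ends, or past the 1-year study duration. If GMT starts more than 30 weeks after the recruiting visit, it will not be finished by then. GMT participants may also have had one extra B-CAM at the early re-test.
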